In the list of *, use a row for an adverse reaction; enter multiple adverse reactions in the equivalent number of rows for a patient. Entry of a patient number, etc. should be repeated.

4) Table for “Patients in the efficacy analysis group”

A table and a chart of changes in HIV-RNA load/CD4	
Prepare a chart and table on the changes in HIV-RNA load/CD4 in patients with and without treatment history, with and without concomitant CYP3A inhibitors, sex, with and without complications, with and without concomitant drugs, CDC classification and for all patients in the efficacy analysis group.
 
Pre-administration (Month 0) should be the most recent date within 30 days before administration including the first administration date.
 
For post-administration (Month 3, 6, 9, etc.), choose the value obtained on the most recent date within ±45 days from each point of Month 3, 6, 9, etc. If a “test value” is missing either before or after administrations, it should not be included in the chart.
 
Use a line chart with test values on the y-axis and months after administration (for every 3 months) on the x-axis.
 
For each point, extend the whisker in a single direction to show the SD value.
 
When you have n=1 for each point, display it with a dot without connecting it with a line.
 
Of note, for the maximum number of HIV-RNA copies detected, replace it with 399 from the initiation of survey to March, 2008, with 39 from April, 2008 to 2010 and with 19 in and after 2011 (depends on the site). Handle the encoded values, etc. as follows: Replace the values with inequality sign with the following [1] to [3] in calculation:

--	--

	
[1] <400: The value that you subtract 1 from the figure without inequality sign. Note that the inequality sign must be removed from the figures with inequality sign. For example: change "<20" to "19", "<40" to "39", "≤20" to "20", "≤40" to "40"
 
[2] ≥400 and <100000: Missing
 
[3] ≥100000: the value without inequality sign. For integer values less than 400 with no inequality sign, use them as they are without replacement.

Patients included in the chart [data in each plot]	Display the patient registration numbers and test results for each point of Month 0, 3, 6, 9, etc. to the number of HIV-RNA copies and CD4, the output data in the above graph.

5) Changes in tropism

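### Undetectable HIV-RNA is set to 39 copies up to 2010 and to 19 from 2011, so a suppressed patient followed across a limit change is recorded with a false fall of 20 copies

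*SAP*

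**What the plan says.** All the rules are in SAP section 4), tables for the efficacy analysis group, in the row on changes in HIV-RNA load and CD4.

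- **By date.** The first part reads "for the maximum number of HIV-RNA copies detected, replace it with 399 from the initiation of survey to March, 2008"; the next two periods are handled "with 39 from April, 2008 to 2010 and with 19 in and after 2011 (depends on the site". The wording speaks of a maximum number of copies detected. Given the examples below, it can only sensibly mean a result at the detection limit.
- **By inequality sign.** Below 400 the rule is "The value that you subtract 1 from the figure without inequality sign", with the examples "change '<20' to '19', '<40' to '39". A result written with `≤` keeps its figure, so `≤40` becomes 40. Signed figures from 400 up to 100,000 become missing, and from 100,000 up only the sign is dropped.
- **Unsigned values.** "For integer values less than 400 with no inequality sign, use them as they are without replacement".
- **Display.** "Use a line chart with test values on the y-axis and months after administration (for every 3 months) on the x-axis". For spread, "extend the whisker in a single direction to show the SD value". The SAP names no log scale, and does not say whether the plotted centre is a mean or a median.
- **Baseline.** "Pre-administration (Month 0) should be the most recent date within 30 days before administration including the first administration date".

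The output is produced for all efficacy patients and by treatment history, CYP3A inhibitor use, sex, complications, concomitant drugs and CDC class. The SAP provides no common floor, no proportion below a common threshold and no sensitivity display.

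**The concern.** The number plotted for an undetectable result depends on when and where the sample was tested, not on the patient. Someone suppressed throughout can be recorded as 39 and later as 19, and the chart has no means of showing that nothing happened.

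Protocol section 8.2(2) tabulates HIV-RNA by background characteristic to look for factors that affect efficacy. If two strata differ in start year or in site mix, they could carry different floors at the same month and differ for that reason alone. The x-axis is time since first dose, so the steps would not line up at one visible point. They would be spread over the first two years, where a gradual decline could be taken for a treatment response.

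**Working it through.** **Inputs from the documents.** Replacement values 399, 39 and 19 (SAP section 4). Earliest first administration date 25 December 2008, earlier dates being moved to it (SAP General Definitions, date conversion). A month is 30 days (same table, date unit). Enrolment ends 31 March 2017 (protocol section 6).

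**Inputs not in the documents, assumed.** *u* = share of patients undetectable at both times; *c* = share of patients with values on both sides of the change.

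**1. The plan's own values.** Replacement = limit − 1: 400 − 1 = 399, 40 − 1 = 39, 20 − 1 = 19. All three are reproduced. The 399 period ends in March 2008, before any usable baseline, so only the step from 39 to 19 matters.

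**2. One patient, undetectable on both sides.**
- Copies: 39 − 19 = 20
- Relative: 20/39 = 51%
- Log scale: log10(39/19) = 0.312

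**3. Who can cross, and when.** From 25 December 2008 to 1 January 2011 is 737 days, and 737/30 = 24.6 months. On the stated dates, only patients who start in that window can cross, each at a personal month between 0 and about 24. If starts were uniform from 25 December 2008 to 31 March 2017 (3,019 days, assumed), *c* = 737/3,019 = 24%. If 2010 means the Japanese fiscal year to March 2011, the figures are 827 days, 27.6 months and 27%.

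**4. Shift in a group mean between Month 0 and late follow-up.** Log scale: *u* × *c* × 0.312. Raw scale: *u* × *c* × 20.

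| *u* | *c* | log10 | copies |
|---|---|---|---|
| 0.5 | 1 | 0.156 | 10 |
| 0.9 | 1 | 0.281 | 18 |
| 0.5 | 0.244 | 0.038 | 2.4 |
| 0.9 | 0.244 | 0.069 | 4.4 |

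**5. Raw mean with some viraemia.** Let 90% be undetectable, 10% be at 10,000 copies (assumed), and everyone cross.
- Before: 0.9 × 39 + 0.1 × 10,000 = 1,035
- After: 0.9 × 19 + 0.1 × 10,000 = 1,017
- Change: 18/1,035 = 1.7%, against an SD of √(0.9 × 0.1) × (10,000 − 39) ≈ 2,990

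If everyone is undetectable, the mean goes from 39 to 19, the full 51%.

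**6. Median.** It falls from 39 to 19 if more than half the patients are undetectable and all of them cross. If most patients start from 2011 on, it can be 19 throughout.

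**7. Conflict between rules.** A `<40` reported in 2011 is 19 by the date rule and 39 by the sign rule. The remark on site dependence does not say which prevails.

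**8. With one floor.** The same patient reads, for example, 39 and then 39: a difference of 0 copies and 0 log10, whatever *u* and *c* are.

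**The case against.** The strongest reply is that the artefact is real but narrow, and on the display that the text suggests it is small. Test values with an SD whisker point to raw means. There the shift cannot exceed 20 copies, and a few viraemic patients swamp it. Patients who start from 2011 on do not cross on the stated dates, and a site that kept its limit shows no step if its results follow that limit. The display is descriptive: the SAP attaches no test, margin or decision rule to HIV-RNA. Protocol section 8.2 lists HIV-RNA beside CD4 and CDC classification without ranking them, and its primary items are adverse drug reactions. All of this stands, and it limits the point's weight.

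Some stronger readings are tempting but not supported:

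- A reader might infer that every patient who stays suppressed appears to improve. Only those with values on both sides of a limit change do.
- A reader might infer that the chart will show a fall, whatever scale is used. The time axis spreads the steps out, and on raw means they may be invisible.
- A reader might infer that strata such as treatment history will differ. No document gives start year or site by stratum, so the most that can be said is that they could.
- A reader might say that an unsigned 25 in 2012 is plotted in the wrong order against an undetectable 39 in 2010. The true value behind `<40` may lie on either side of 25, so the order is unknown, not shown to be wrong.

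It can also be said that limit minus 1 follows what each laboratory reported, and that a common floor discards genuine values of 20 to 39. The second part is a real cost. The first does not help a chart meant to show change within patients.

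**Conclusion.** The point holds for suppressed patients followed across a limit change, and the per-patient size is certain because it follows from the SAP's own replacement values. Nothing elsewhere in the documents corrects it.

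The size for a group is not known. The range of 0.16–0.28 log10 assumes that everyone crosses, and should not be quoted without that condition. Under uniform starts it is roughly a quarter of that, and starts concentrated in the early years would raise it. The effect deserves attention in largely suppressed strata or if a log or median display is chosen, which the SAP leaves open. The undecided order of the date and sign rules is a separate, smaller gap: two programmers could produce different tables from the same data. Together these justify a cheap correction to a descriptive output. They do not cast doubt on the survey's safety results.

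**What to change.** In the HIV-RNA chart and table, replace the date-based values with one rule for all dates and sites:

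- Set every result at or below 40 copies to one stated value (for example 39). This covers `<20`, `≤20`, `<40`, `≤40`, not detected, and any unsigned value up to 40. The `≤40` case must be named, because the SAP now sets it to 40.
- Treat a result reported as below a limit higher than 40 as missing in the chart, and flag it in the listing. The existing rule for signed figures from 100,000 up can stay.
- Keep the original results in the plot-data listing.

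This also settles which rule prevails. No new data are needed, only a short SAP edit and a small programming change. The costs are that differences below 40 copies are no longer visible in the chart, and that any result censored above 40 drops out of it. Because the SAP leaves out of the chart a test value that is missing before or after administration, a Month 0 result lost in this way could remove that patient. The number so affected should be reported.

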8.2 Analysis Methods

(1) Analyses related to safety evaluation

In the safety analysis set, the primary analysis items will be the occurrence of common ADRs and the incidence of ADRs (proportion of patients with AEs with which Celsentri's causal

relationship could not be denied). In addition, when tabulating the incidence of ADRs by factor such as patient background characteristics, factors affecting the onset of ADRs will be also examined.

(2) Analyses related to efficacy evaluation

Efficacy parameters for anti-HIV drugs such as a CD4 count, number of HIV-RNA copies and CDC classification will be tabulated and analyzed by patient background characteristic to examine factors affecting the efficacy of Celsentri. In patients tested for tropism, the relationship with the status of tropism change will be also evaluated.

9. Organization System for the Implementation of the Survey

The survey will be conducted using the system described in Appendix 3 in accordance with the procedures for the implementation of the HRD cooperative investigation (Appendix 2). The procedures for notifying ADRs, etc. are presented in Appendix 4.

This survey will be performed as a cooperative investigation by companies marketing drugs for the treatment of HIV infection^{Note 1)} using a common CRF. The common CRF for the drug use-results survey may be completed one copy for one patient even if a few anti-HIV infection drugs are coadministered during the reexamination period.

10. Name and Address of the Contractee, and the Scope of the Concerned Outsourced Activities

(1) Contractee

Address: PPD [redacted]

Name: PPD [redacted], PPD [redacted] CMIC PMS Co., Ltd.

Name of the person responsible for implementation: PPD [redacted], Postmarketing Surveillance Operation Implementation Supervisor

(2) Scope of outsource activities

- 1) Request to and contract with institutions
- 2) Issuance of a user's ID and password to each investigator
- 3) Retention of the originals of enrollment forms
- 4) Sending the copies of enrollment forms
- 5) Verification of registration and investigation items entered and sent by the investigators
- 6) Collection of the originals of CRFs
- 7) Preparation and collection of the statement of confirmation
- 8) Sending the copies of CRFs
- 9) Arranging reinvestigation items
- 10) Request for a reinvestigation
- 11) Retention of the originals of CRFs
- 12) Sending the CRFs (final version)
- 13) Data locking
- 14) Coding
- 15) Data tabulation/analyses

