Tropism classification at the first administration of CELSENTRI Tablets.	Display the value obtained on the closest date to the first administration date of CELSENTRI Tablets within 30 days before/after the first administration. Display the earlier value obtained for this if the same values are found on the same dates both before and after the first administration. [Stratification] R5, X4, DM, NR, Not implemented* *If it was not conducted, separately record the reason for this (Prepare a list of the reasons why the tropism assay was not conducted).
Presence/absence of concomitant treatment	If any concomitant treatment was given in the “administration period” of CELSENTRI Tablets (for ≥1 day), select “present”. [Stratification] Absence, Presence, Unknown/not provided
Presence/absence of blood coagulation factor	Count the presence/absence of drugs administered while the patient was on CELSENTRI Tablets 150 mg (the drugs with the concomitant drug codes {6343406, 6343409, 6343429, 6343430, 6343414, 6343431, 6343432, 6343434} on the top). In addition, display the presence/absence when “present” was selected for the presence/absence of haemophilia. [Stratification] Absence, Presence, Unknown/not provided

*When the minimum/maximum are specified in the stratification of the mock-up, display the minimum/maximum of each item.

<<Handling of cases>>

Patients whose survey form was collected	On March 26, 2018, the data on all the patients registered during this survey period were locked. Therefore, they are the patients whose survey form was collected as of March 26, 2018.
Patients in the safety analysis group	
Patients excluded from the patients applicable to the following [Exclusion criteria from the safety analysis group] (Note that the patients with adverse reactions are not excluded).
 
[Exclusion criteria from the safety analysis group]
 
[1] Not visited after the first visit ⇒Patients whose survey form is composed of 1 volume alone, with “Outcome of patient” of “1. Not visited” or “2. Transferred”, and also with their first administration of CELSENTRI Tablets = the outcome confirmation date in “Outcome of patient”.
 
[2] Not administered ⇒Patients whose administration of CELSENTRI Tablets cannot be traced since the approval date (=December 25, 2008).
 
[3] Unable to re-survey adverse events ⇒ “8 Unknown” and “0. Not provided” for the presence/absence of adverse events”

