For the patients who underwent a tropism assay (the patients whose tropism had been classified when the administration was started), prepare a list of their tropism assay results obtained within ±45 days of each point at Month 3, 6, 9, etc. of administration.

NOTE: These table forms may be subject to change due to the aggregated results or the relevant system.

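### The protocol commits to evaluating a relationship with tropism change, but the SAP specifies only a list of assay results, and its two-sided baseline window lets a nearer on-treatment result replace an available pre-dose one

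*SAP*

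**What the plan says.** **Protocol 8.2(2), efficacy evaluation.** The first sentence deals with efficacy parameters, CD4 among them, and includes this: "number of HIV-RNA copies and CDC classification will be tabulated and analyzed by patient background characteristic to examine factors affecting the efficacy of Celsentri". The next adds: "In patients tested for tropism, the relationship with the status of tropism change will be also evaluated". It does not name the second variable.

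**SAP, 5) Changes in tropism.** The analyst is to "prepare a list of their tropism assay results obtained within ±45 days of each point at Month 3, 6, 9, etc. of administration". Those listed are "the patients whose tropism had been classified when the administration was started". Nothing else is asked for.

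**SAP, 4) Table for the efficacy analysis group.** HIV-RNA and CD4 are tabulated and charted by treatment history and concomitant CYP3A inhibitors, then by "sex, with and without complications, with and without concomitant drugs, CDC classification and for all patients in the efficacy analysis group". A companion output gives the underlying values: "Display the patient registration numbers and test results for each point of Month 0, 3, 6, 9, etc".

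**SAP, Handling of items, Tropism classification at the first administration.** The rule is: "Display the value obtained on the closest date to the first administration date of CELSENTRI Tablets within 30 days before/after the first administration". When a result before and a result after the first dose are equally distant, the earlier one is used. The categories are R5, X4, DM, NR and not implemented.

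**SAP, General Definitions and section 4.** The definition of prior to administration, and Month 0 for HIV-RNA/CD4, both look back 30 days and stop at the day of the first dose.

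**The concern.** A relationship needs two variables, and the SAP's tropism output contains one. The drug is indicated for CCR5-tropic infection, and one protocol objective is to find factors likely to affect efficacy. How virological and immunological response runs in patients whose tropism shifts is therefore a question one would expect the survey to answer. As specified, the answer depends on someone joining lists afterwards with a definition of change chosen at that point.

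The baseline rule raises a separate problem. A starting classification taken during treatment may already reflect a shift. The SAP avoids this for HIV-RNA and CD4 but not for tropism, and the same derived value is a background item in two other tables.

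**Working it through.** **1. Is the evaluation specified anywhere in the SAP?** The outputs that could carry it are:

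- Patient composition ratio: tropism class at first administration. This is a baseline class, not change.
- Incidence of adverse reactions per patient background: the same baseline class. This is safety, not efficacy.
- List of reasons why the assay was not conducted: no assay result.
- HIV-RNA/CD4 tables and charts: strata are treatment history, CYP3A inhibitors, sex, complications, concomitant drugs and CDC class, which makes 6, plus all patients. Tropism strata: 0.
- HIV-RNA/CD4 values by patient and Month: no tropism.
- Changes in tropism: assay results by Month, with no response variable and no definition of change.

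No output puts tropism change beside HIV-RNA, CD4 or CDC class.

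**2. Which days can each rule see?** Inputs: 1 month = 30 days (SAP, Date unit); follow-up windows of ±45 days; baseline window of ±30 days. I take the first-dose date as day 0; counting it as day 1 moves the day labels by one.

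Month m is centred on day 30m, with window 30m - 45 to 30m + 45:

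- Month 3: 90 - 45 = 45 to 90 + 45 = 135
- Month 6: 135 to 225
- Month 9: 225 to 315
- Month 12: 315 to 405

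The first follow-up window opens on day 45, so post-dose days 1 to 44 are outside the follow-up list. Days 1 to 30 can serve only as baseline or go unused. Days 31 to 44, that is 44 - 31 + 1 = 14 days, lie in no tropism window. Adjacent windows share days 135, 225 and 315.

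**3. Which result becomes baseline?** The rule takes the smallest distance from day 0, and the earlier result on a tie.

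- Days -20 and +10: 10 < 20, so day +10 is taken (on treatment).
- Days -30 and +29: 29 < 30, so day +29 is taken (on treatment).
- Days -10 and +10: equal, so day -10 is taken.

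For a pre-dose assay on day -20, any post-dose assay on days 1 to 19 displaces it. The tie rule protects the pre-dose result only when the distances are equal. Under the look-back used for HIV-RNA/CD4 Month 0, the pre-dose result would be kept in all three cases.

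**4. Consequence.** Take R5 on day -20, DM on day +10 and DM on day 90. The derived baseline is DM, and that is the class counted in the composition and adverse-reaction tables. If the same value is the starting point for change, this patient shows none; from the pre-dose result the sequence is R5 to DM.

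**5. Reset dates.** The SAP's date conversion replaces a first dose before approval with the approval date, 25 December 2008. For such a patient, a result dated 25 November to 25 December 2008 counts as pre-dose although treatment may already have begun.

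**The case against.** The protocol sentence promises an evaluation, not a table, and leaves the second variable open. The SAP does have a tropism output, and it lists HIV-RNA/CD4 by patient at the same Months. In a descriptive survey with few retested patients, reading the lists together might be thought enough. Part of this stands: linking a response to efficacy is an interpretation, though the natural one given the heading and the preceding sentence, and matching by hand is possible. But matching is not specified, and without a definition of change two analysts could classify the same patient differently.

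Several stronger readings are tempting and not supported:

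- A reader might infer that the tropism list is defective because it has no rule for several assays in one window. A list can show them all. The HIV-RNA/CD4 chart needs its rule ("choose the value obtained on the most recent date within ±45 days from each point of Month 3, 6, 9, etc") because it uses one value per patient and point.
- A reader might infer that the list itself will print a wrong starting value. It uses classification at start to say who is listed, names no baseline column, and the mock-ups are not in the text. The effect on change is therefore conditional.
- A reader might take the number of date combinations in which the post-dose result wins as a rate in patients. It is not one, since the documents give no retest frequency.

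The two-sided window may also be deliberate: the item is labelled as at first administration, and the window keeps patients who have only an early post-dose assay. That supports using such results when nothing else exists, not preferring them to a pre-dose result. Finally, the gap before day 45 is shared with HIV-RNA/CD4 follow-up and is not peculiar to tropism.

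**Conclusion.** The main point holds without conditions beyond the natural reading of Protocol 8.2(2): the SAP, followed as written, yields no planned summary relating tropism change to efficacy, and it does not define change.

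The baseline point holds as a possibility. It requires a patient with assays on both sides of the first dose within 30 days, the later one nearer, and a different class between them. Where that occurs, baseline tropism is misclassified in the composition and adverse-reaction tables. An early shift is hidden only if the same value is used as the starting point for change.

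The sizes that can be stated are the windows: days 1 to 44 never appear as follow-up, and 14 of those days are in no tropism window. The number of patients affected and any effect on HIV-RNA or CD4 cannot be computed, because the documents give neither the tropism mix nor the retest frequency. The SAP should be corrected, but nothing here shows that the survey's other results are wrong.

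**What to change.** 1. **Define change and tabulate it.** Define tropism change as R5 at baseline and X4 or DM later. Show NR, and patients starting as X4 or DM, as separate categories. In the efficacy analysis group, add one descriptive table of HIV-RNA and CD4 at each Month by change status (no change, changed, not retested or not evaluable), with the number of patients in each. For this table only, state which assay is used when a window holds several, and assign days 135, 225 and 315 to one Month each.
2. **Prefer a pre-dose baseline.** Use the closest pre-dose result, first-dose day included, when one exists. Use a day 1 to 30 result only when none exists, and flag it, so that no patient is lost from the list. Also flag patients whose first-dose date was reset to the approval date.
3. **Keep the early results.** List post-dose results on days 1 to 44 that are not used as baseline.

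Baseline tropism as a further stratum of the HIV-RNA/CD4 tables is optional; the protocol does not promise it.

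The cost is SAP wording, one table, two flags and a few listing rows. Protocol 7.7 already collects tropism with test dates, so no new data are needed. The limits remain: strata will be small, change is known only in retested patients, flagged baselines cannot be read as untreated values, and the table is descriptive only.
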